Clinical Study Protocol

Anti-platelet Precision Medicine to Prevent Stroke Early Progression and Recurrence (PRECISE)

Protocol Number	PRECISE
Protocol Version	3.1
Version Date	July 23, 2018
Study Center	Asan Medical Center and 21 Other Institutions
Study Coordinator	[name], Dept. of Neurology, Asan Medical Center

Confidentiality Statement

This document contains confidential information that must not be disclosed to anyone other than the principal investigator, investigators, the IRB and national regulatory authorities without prior written consent of the sponsor, except to obtain informed written consent to participate in the study from those providing the information of what is intended to be observed in the study.

※ PROTOCOL SYNOPSIS

Study title	Anti-platelet Precision Medicine to Prevent Stroke Early Progression and Recurrence (PRECISE)
Study phase and design	Pragmatic, multi-center, non-interventional, non-random trial based on prospective observational study
Study center	Asan Medical Center and 21 other institutions
Study coordinator	[name] of Department of Neurology, Asan Medical Center
Study sponsor	[name] of Department of Neurology, Asan Medical Center
Study funder	Chong Kun Dang Holdings
Study objectives	
Primary objectives: To predict the clinical prognosis according to the antiplatelet treatment regime (aspirin as first-line treatment or in combination with clopidogrel), develop an AI that will search for and retrieve similar cases to each patient, and assess benefits of the technology:
 
 1) To establish a stroke clinical-imaging library (big data) and develop Deep Learning-based AI that understands the relationship between anti-platelet agents and prognosis (progression or recurrence). AI will present the probability of stroke progression or recurrence following each treatment regime. AI will also help physicians make treatment decisions by searching for and retrieving existing cases with similar clinical conditions to the patients concerned. 2) To prove AI's merit in predicting prognosis by applying it to different patient groups. 
Secondary objective: To analyze practical results of antiplatelet agents: The aspirin alone group and the clopidogrel plus aspirin group will be compared against each other directly to help find the link between early progression and recurrence of stroke. Although this is a non-randomized trial, different statistical methodologies, including propensity score matching (PSM) should address confidence issues.

Study subjects	Acute ischemic stroke patients: Transient ischemic attack with confirmed acute ischemic stroke by brain imaging

Inclusion criteria	1) Male and/or female subjects who are aged 19 or over. 2) Patients with acute noncardiac stroke or transient ischemic attack within 72 hours of the onset (in the case of a transient ischemic attack, presence of ischemic/ischemic lesion on DWI or PWI). 3) Patients whose informed consent document within 72 hours of onset was signed and submitted. 4) Patients who were treated with aspirin alone or aspirin plus clopidogrel resinate following stroke.								
Exclusion criteria	1) Patients who need anticoagulants for cardiac ischemic stroke or other reasons. 2) Patients who suffered severe stroke (National Institutes of Health Stroke Scale > 16). 3) Patients who received emergency remission therapies such as tPA and thrombolysis. 4) Patients with neurological deterioration prior to signing an informed written consent document. 5) Patients who have undergone patency procedures (surgery or stent insertion) in the cerebrovascular or carotid arteries following stroke or are expected to do so. 6) Patients who are scheduled to undergo major surgery. 7) Patients who developed stroke during procedure/surgery. 8) Patients with recent history (in the past three months) of cerebral hemorrhage. 9) Patients with active internal bleeding. 10) Patients with severe anemia (Hb <10 g / dL) or bleeding tendency (platelet <100,000 / uL or PT-INR > 1.7). 11) When a patient's life expectancy is less than 6 months due to other systemic disease.								
Number of target study subjects	
  
 	Aspirin alone group	Aspirin + Clopidogrel resinate group	Total No. of target subjects	
   
 No. of subjects	1,000	1,000	2,000	
  
		Aspirin alone group	Aspirin + Clopidogrel resinate group	Total No. of target subjects	No. of subjects	1,000	1,000	2,000
	Aspirin alone group	Aspirin + Clopidogrel resinate group	Total No. of target subjects						
No. of subjects	1,000	1,000	2,000						
Study duration	1) Study duration: Approximately 36 months from IRB approval (subject to change depending on subject enrollment speed) 2) Study duration for each subject: 90 days (\pm 15 days)								
Study drug and dose	
  
 Study drug	Route of administration/dose	
   
 Aspirin (monotherapy or concomitant therapy)	75~100mg once per day, initial loading dose of 300~500mg/d is allowed	
  
	Study drug	Route of administration/dose	Aspirin (monotherapy or concomitant therapy)	75~100mg once per day, initial loading dose of 300~500mg/d is allowed				
Study drug	Route of administration/dose								
Aspirin (monotherapy or concomitant therapy)	75~100mg once per day, initial loading dose of 300~500mg/d is allowed								

	
Clopidogrel resinate (Concomitant therapy)
 
75mg once per day, initial loading dose of 300mg/d is allowed

Study description	
This is a pragmatic, multi-center, non-interventional, non-randomized prospective observational study.
 
■ Study procedures
 
This is a prospective study of patients with acute stroke or transient ischemic attack within 72 hours of symptom onset. It is to mainly observe the patients' prognosis following the prescription of clopidogrel resinate and aspirin, collect relevant data and create big data for stroke. Based on this data, an AI, using various advanced statistical methodologies and deep learning techniques will be developed, and offer information regarding stroke prognosis by extracting markers that are characteristic of the relationship between stroke and the study drug.
 
These analyses and results will include information on which drug regimen will better prevent the progression or recurrence of stroke by considering individual patient conditions. This is a pragmatic trial based on the prescription and treatment processes of routine clinical practice. Thus, there is no major restriction and with only the minimum exclusion criteria in place, it does not hinder usual clinical practices. Therefore, selecting and changing a patient's antiplatelet agents should be a rational medical judgment made by the patient's attending physician. The study will proceed without any major change in the sequence of routine clinical examinations, prescriptions, treatments, observations, etc. Provided, the process of storing and analyzing relevant information will be added to each study procedure in accordance with study methodologies and conditions no other special efforts or limitations will be required.
 
The data will be collected prospectively, and the AI will generate brain imaging data and prognostic indicators for 3-months after stroke has occurred. The performance of the AI will be verified with independent test sets.

Dropout criteria	
Because the subjects will receive usual stroke care practice, there will be no subject withdrawal or dropout due to issues related to the study description and design.
 
However, if a research subject withdraws his/her consent to participate in the study (informed consent to have his/her personal information utilized), participation of the research subject will be suspended, and the data concerned

	will not be used in the study.
Endpoints	
Primary study endpoints
 
AI will learn and predict the occurrence of the following outcome variables (up to 3 months after stroke onset) according to the antiplatelet regimen (aspirin alone, or aspirin plus clopidogrel). An independent investigator, without knowledge of individual patient treatment regimens, will evaluate the same outcome variables separately and compare the results with those predicted by the AI:
 
 1) Neurological deterioration 2) New ischemic stroke 3) Symptomatic hemorrhagic transformation of an ischemic stroke 4) Symptomatic intracranial hemorrhage 5) Myocardial infarction 6) Coronary revascularization without myocardial infarction 7) Major hemorrhage other than intracranial hemorrhage (life threatening or non-life-threatening) 8) Minor hemorrhage other than intracranial hemorrhage 9) Ischemic vascular death 10) Hemorrhagic vascular death 11) Other serious adverse events 
Secondary study endpoints
 
A direct comparison between the aspirin alone group and the aspirin and clopidogrel combination therapy group for the incidence of 11 outcome variables evaluated by an independent investigator at the primary endpoints will be conducted.

Statistical Methodology	
General principle
 
All the enrolled study subjects whose results are confirmed will be subject to analysis, and they will be selected and classified according to the study methodologies and objectives prior to analysis. During the study period, data will be regularly checked and managed so that the number of datasets and their levels will be maintained appropriately.
 
Analyses of endpoints
 
Analysis of primary endpoints
 
 1) The stroke clinical and imaging library (big data), that includes all the

	
clinical/imaging information related to clinical prognoses, will be established, and based on a deep learning algorithm, AI that has learned the relationship between antiplatelet agents and the following prognostic information will be developed.
 
 2) A probability of prognosis according to each treatment option prior to using antiplatelet agents will be offered. This information will help physicians select an antiplatelet agent by searching for and retrieving similar cases that match each patient. 3) The stroke clinic and imaging library (big data) regarding the effect of antiplatelet agents that are being prescribed mainly to stroke patients in the clinical setting and the prognostic information of the patients concerned will be constructed. The relationship and prognostic features of antiplatelet agents in preventing early progression and recurrence of stroke will be extracted and analyzed from the “Big Data.” 4) The development of AI using deep learning techniques will provide the basis for analysis of internal and external variables of stroke. This technique will change the model composition in line with the features and numbers extracted from the data. The depth and structure of the model will segment and materialize the characteristics of the target subjects and will be accompanied by the optimal design and verification processes of the model to simultaneously consider clinical/image information. 5) The research analysis using the trained AI that will be developed will need to have its results clearly verified as to their quality/accuracy. The delivered outcome will be used directly or indirectly by physicians, but the performance and reliability of the results that will be generated are of significant importance. Therefore, the AI will learn and have its performance assessed based on the data that will continue to accumulate throughout this study. However, because of the features of deep learning technology, training and verification, using the same data may cause major issues such as overfitting. Therefore, a new dataset will be created to evaluate the performance of the AI. 
Analysis of secondary endpoints
 
 1) The propensity score matching (PSM) technique will be used to select either the aspirin monotherapy, or the clopidogrel resinate and aspirin combination therapy group which have matched important clinical/imaging parameters that affect the prognosis of stroke.
--	---

	2) Compare the prognosis of each treatment group to determine which prescription method is superior.
--	--

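### The deterioration risk offered before treatment is learned only from patients still deterioration-free at consent, which may come up to 72 hours after onset, and the protocol does not say so

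*Protocol*

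**What the plan says.** All places are in the Protocol Synopsis.

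- **Exclusion criteria, item 4:** the study excludes "Patients with neurological deterioration prior to signing an informed written consent document".
- **Inclusion criteria, item 3:** it enrols "Patients whose informed consent document within 72 hours of onset was signed and submitted". Entry can thus fall anywhere from 0 to 72 hours after onset.
- **Endpoints, primary:** the AI is to predict the "following outcome variables (up to 3 months after stroke onset) according to the antiplatelet regimen". Neurological deterioration is the first of the eleven, and the window is counted from onset.
- **Endpoints, secondary:** the two regimens are compared directly on the "incidence of 11 outcome variables evaluated by an independent investigator at the primary endpoints will be conducted". Analysis of secondary endpoints, item 1, adds propensity score matching on important clinical and imaging parameters. Onset-to-consent time is not named.
- **Study objectives, primary objective 1:** "AI will present the probability of stroke progression or recurrence following each treatment regime".
- **Analysis of primary endpoints, item 2:** "A probability of prognosis according to each treatment option prior to using antiplatelet agents will be offered", and its use is stated: "This information will help physicians select an antiplatelet agent by searching for and retrieving similar cases that match each patient".

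None of these places says that the deterioration results apply to patients who have reached a given hour without deteriorating.

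**The concern.** The outcome clock starts at onset, but a patient can contribute a deterioration event only after consent, having been free of it until then. In statistical terms, deterioration is left-truncated at a patient-specific time between 0 and 72 hours. The prediction is meant for an earlier moment, before antiplatelet treatment is chosen.

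This differs from an ordinary eligibility limit. The NIHSS limit in exclusion 2 can be checked when the agent is chosen. Whether a patient will still be deterioration-free at some later consent hour cannot.

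At stake is the calibration of a risk that physicians are to use in selecting a regimen, in a study whose title names early progression. The deterioration incidence would also depend partly on how quickly consent was obtained.

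**Working it through.** **No plan figure to reproduce.** The protocol gives no deterioration rate, no distribution of consent times, and no inputs behind its 1,000 per group.

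**Direction.** Let S(t) be the probability of being deterioration-free t hours after onset, and let consent timing be unrelated to risk.
- Risk seen in enrolled patients who consent at hour c: 1 − S(90 d)/S(c).
- Risk of a patient assessed earlier, at t0 < c: 1 − S(90 d)/S(t0).

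Since S(t0) ≥ S(c), the first cannot exceed the second, and it is smaller whenever deterioration occurs between t0 and c. This needs no assumed rate.

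**Size, on assumed inputs.** Let R be the 90-day risk from onset and s the share of it falling in the first 72 hours at an even rate. The risk from hour h in those deterioration-free at h is

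(R − R·s·h/72) / (1 − R·s·h/72).

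With R = 0.10 and s = 0.6, at h = 6: (0.10 − 0.005)/(1 − 0.005) = 9.55%. At 12, 24, 36 and 48 hours it is 9.09%, 8.16%, 7.22% and 6.25%.

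If consents are spread evenly over 0-48 hours, the cohort average is 1 − (1 − R)·[−ln(1 − k)]/k with k = R·s·48/72 = 0.04. This gives 1 − 0.9 × 1.0206 = 8.15%. An AI that ignores timing would return about this value for everyone:

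| Early share s (R = 10%) | Cohort average | True risk at 6 h | Predicted/true at 6 h | Predicted/true at 48 h |
|---|---|---|---|---|
| 60% | 8.15% | 9.55% | 0.85 | 1.30 |
| 30% | 9.09% | 9.77% | 0.93 | 1.11 |
| 3.3% (72 of 2,160 h, near-constant hazard) | 9.90% | 9.97% | 0.99 | 1.01 |

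At a 24-hour decision the ratio is 1.00 in all three rows. Across R of 5-15% and s of 40-80%, it is 0.79-0.91 at 6 hours and 1.16-1.55 at 48 hours. With consents spread over 0-72 hours (R = 10%, s = 60%), it is 0.75 at 6 hours.

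A more front-loaded curve gives more. Take S(t) = exp(−H(1 − exp(−t/m))) with 10% risk and consents over 1-72 hours. The pooled risk is 5.3% against 8.9% from 6 hours for m = 48 h, and 3.2% against 7.9% for m = 24 h.

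**Regimen comparison.**
- *Equal timing* (0-48 h in both groups): a true hazard ratio of 0.75 appears as a risk ratio of 0.76, so there is practically no distortion.
- *Different timing, no drug effect* (24 v 36 h): the unmatched risk ratio is 7.22/8.16 = 0.88. A two-sided 5% test with 1,000 per group rejects in about 12% of trials.

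**Check of the remedy by simulation** (2,000 runs, 1,000 per group, consent 0-48 v 12-60 h, consent timing unrelated to risk):

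| True HR | Risk ratio from simple proportions | Delayed-entry HR |
|---|---|---|
| 1.00 | 0.89 (12.6% rejection) | 1.01 (5.1% rejection) |
| 0.75 | 0.66 | 0.74 |

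**The case against.** The strongest reply is that the protocol does not commit to the faulty analysis. It says incidence, not crude proportion. It allows several statistical methods, and nothing rules out delayed entry or time since onset as a covariate. Such details commonly sit in a statistical analysis plan, which is not at hand. This stands: a reader might infer that an unadjusted proportion is fixed, and the text does not support that. What an analysis plan would not settle is the protocol's own description of whom the probability serves and when. Eligibility, outcome clock and intended use are all set here.

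Second, the AI may learn timing, since the library is to hold all prognostic clinical and imaging information. It may, and the ratios above then shrink. They describe a timing-blind model, which the protocol neither plans nor excludes. Even a model using timing cannot be supported for hours before the earliest consents.

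Third, independent test sets are planned. If these patients are enrolled under the same exclusion, they share the truncation and the AI would look calibrated. The source of the new dataset is not stated.

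Fourth, the effect may be small. This also stands: it depends on how strongly deterioration clusters early, which the protocol does not quantify.

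A reader might also infer that the regimen comparison is biased. That requires consent timing to differ by regimen and to be left unadjusted. The non-randomized design permits a difference, but nothing in the protocol shows one.

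**Conclusion.** The point holds as a mismatch between who is observed and who is to be advised. Deterioration is recorded only in patients deterioration-free at consent, while its probability is offered before treatment without that condition. The direction for patients assessed before the cohort's consents follows from the design, provided consent timing is unrelated to risk. A model that ignores timing would also overstate the risk for patients still deterioration-free later.

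The size cannot be derived from the protocol. On the main set of assumptions, predicted over true risk at 6 hours runs from 0.85 to about 0.99 as the early share falls from 60% to a near-constant hazard. Steeper early curves give a larger gap. The finding does not make exclusion 4 wrong and concerns deterioration only, not the counting of the other ten outcomes. It does not establish bias between regimens. It merits correction because the affected figure is meant to guide drug choice.

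**What to change.** Keep exclusion 4 and change the following for neurological deterioration only.

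1. In primary objective 1, in item 2 of the primary analysis and in the secondary endpoint, state that the probability and the comparison apply to patients without deterioration at a stated hour since onset.
2. Give the AI that hour as an input: the consent hour in the cohort, the decision hour for a future patient. Give no probability for hours that the cohort's consents do not cover.
3. Compare regimens on the time-since-onset scale with delayed entry at consent. This already handles differing entry times, so onset-to-consent hours need not enter the propensity score. They should not enter it where treatment preceded consent, because they are then post-treatment.
4. State as a limitation that deterioration before consent, including on treatment, is not captured.

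**Cost.** Onset and consent times are already needed to verify inclusion 3, but the date and hour of early deterioration must also be recorded. The AI claim becomes narrower, and estimates for the earliest hours rest on few patients. Delayed entry needs overlapping consent times in the two groups and assumes that consent timing is unrelated to risk given the covariates.

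### The primary check can validate the AI's prognosis under the regimen received, but not by itself the between-regimen difference that physicians are offered for choosing a drug

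*Protocol*

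**What the plan says.** All references are to the protocol synopsis.

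**The use.** Under Study objectives, primary item 1: "AI will present the probability of stroke progression or recurrence following each treatment regime", and "AI will also help physicians make treatment decisions by searching for and retrieving existing cases" that resemble the patient. The Study description adds: "These analyses and results will include information on which drug regimen will better prevent the progression or recurrence of stroke", taking the individual patient into account. Item 2 of the analysis of primary endpoints again offers a probability under each option before treatment, as a help in selecting the agent. Item 5 expects physicians to use the output directly or indirectly.

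**The check.** Under Endpoints (Primary study endpoints), an independent investigator who does not know the regimens "will evaluate the same outcome variables separately and compare the results with those predicted by the AI". Primary objective item 2 is to prove the AI's "merit in predicting prognosis by applying it to different patient groups". The Study description adds: "The performance of the AI will be verified with independent test sets". Item 5 of the analysis of primary endpoints calls for a new dataset because of overfitting.

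**The allocation.** The study is observational. On selecting and changing treatment, the Study description says that "antiplatelet agents should be a rational medical judgment made by the" patient's own doctor.

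**The handling of confounding.** It is stated under the secondary objective: "Although this is a non-randomized trial, different statistical methodologies, including propensity score matching (PSM) should address confidence issues". Propensity score matching then appears under the analysis of secondary endpoints, as a comparison of the two treatment groups.

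**The concern.** Two different quantities are in play. One is the risk of a patient who was in fact given a certain regimen. The other is the difference in risk for the same patient under one regimen or the other. The primary check concerns the first. A physician who sees two probabilities side by side will read the second.

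Where doctors choose the drug, the two quantities agree only if everything that drives both prescribing and outcome is captured and modelled. The planned comparison cannot show whether that is so. A good result on the primary endpoint would demonstrate prognostic accuracy, yet as worded it could be cited in support of a treatment difference that was not tested.

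**Working it through.** The protocol gives no figure to reproduce here: no event rate, accuracy metric or test-set size. Its only size figure is 1,000 + 1,000 = 2,000 patients. The point is one of design logic, and every rate below is an assumption made to illustrate it.

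**Step 1: the mechanism, checkable by hand.** Assume that half the patients carry an uncaptured risk factor. Risk on aspirin alone is 15% with it and 5% without it, and the combination has a true risk ratio of 0.8. The average risk is 0.5 × 15 + 0.5 × 5 = 10% on aspirin and 0.8 × 10 = 8% on the combination, so the true difference is −2.0 points.

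Let a share p of the high-risk patients and 1 − p of the low-risk patients receive the combination. A model that matches the observed risk in each arm predicts:

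- combination: 0.8 × [15p + 5(1 − p)] = 4 + 8p
- aspirin alone: 15(1 − p) + 5p = 15 − 10p
- implied difference: 18p − 11

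| p | Aspirin, predicted = observed | Combination, predicted = observed | Implied difference | True difference |
|---|---|---|---|---|
| 0.5 | 10.0% | 8.0% | −2.0 | −2.0 |
| 0.6 | 9.0% | 8.8% | −0.2 | −2.0 |
| 0.4 | 11.0% | 7.2% | −3.8 | −2.0 |
| 0.7 | 8.0% | 9.6% | +1.6 | −2.0 |
| 0.3 | 12.0% | 6.4% | −5.6 | −2.0 |

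Prediction and observation agree exactly in every row, whatever the error in the difference. A new test set with the same prescribing pattern gives the same agreement.

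**Step 2: a graded version with a recorded predictor.** X is recorded and U is not; both are standard normal. T = 1 is the combination.

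- Prescribing: logit P(T = 1) = 0.5X + gU
- Outcome: logit risk = −2.6 + X + bU + T × ln(0.75)
- Implied difference: the mean over X of P(Y | X, T = 1) − P(Y | X, T = 0)
- True difference: the mean over X and U of the risk under T = 1 minus the risk under T = 0

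| Size of g, b | True | Higher-risk patients get the combination (g > 0) | Lower-risk patients get it (g < 0) |
|---|---|---|---|
| 0.3, 0.3 | −2.1 | −1.5 | −2.8 |
| 0.25, 0.5 | −2.2 | −1.2 | −3.1 |
| 0.5, 0.5 | −2.2 | −0.4 | −4.0 |
| 0.25, 1 | −2.3 | −0.3 | −4.3 |
| 0.5, 1 | −2.3 | +1.5 | −6.2 |

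The table values come from numerical integration. Simulations of 2 million patients with a fitted logistic model gave, for g > 0 in the same order, −1.40 to −1.56, −1.18 to −1.34, −0.34 to −0.49, −0.31 to −0.41 and +1.40 to +1.48. In the four milder rows with g > 0 the fitted model still picked the truly lower-risk arm for 97–100% of patients.

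In the last row U has the same coefficients as X, so the unrecorded factor is as strong as the main recorded one. Even there, with g > 0, predicted against observed risk was 8.4 against 8.4% on aspirin alone and 13.2 against 13.3% on the combination.

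**Step 3: the other safeguards.** The independent test sets and the new dataset are stated for performance and overfitting. Propensity score matching is stated for the secondary comparison of groups. Neither is described as a test of the AI's predicted difference.

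**The case against.** The strongest reply is that the protocol already separates the two questions. The objective that says what is to be proved about the AI speaks of prognosis, the primary endpoint is prediction, and the question of which regimen is superior goes to the secondary matched comparison. No passage says that the primary comparison establishes a treatment difference. This stands, and it is why the check should stay. But primary objective item 1 and item 2 of the primary analysis sit under primary headings and offer the output for choosing an agent. The sentence in the Study description may also cover the matched analysis, though its reference to the individual patient points to the AI as well.

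A second reply is that the library is meant to hold all clinical and imaging information related to prognosis, so the model may adjust well, and that modelling and metrics may sit in an unseen SAP. That is fair. The AI's difference could be right. The primary comparison still could not show it, and an SAP would not change the uses stated here.

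A reader might also infer more than the documents support:

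- *That the AI will point to the wrong drug.* No confounding has been shown. In the table above, reversal needs an unrecorded factor as strong as the main recorded one.
- *That bias would usually hide a benefit.* This depends on assuming that higher-risk patients get the combination. The documents give no direction, and the opposite assumption exaggerates the benefit.
- *That the check would select a confounded model over a correct one.* The protocol plans no contest between models.
- *That confounding is ignored.* It is acknowledged, but only for the secondary comparison.

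**Conclusion.** The concern holds as a mismatch between the stated check and the stated use. The primary comparison is adequate for prognosis under the regimen received and by itself uninformative about whether the between-regimen difference is right. Under the assumed inputs, a true difference of about −2 points could appear as anything from +1.5 to −6.2 without disturbing calibration in either arm. The milder settings give about −1.5 to −0.3 in one direction and −2.8 to −4.3 in the other. These figures rest on an assumed risk level, effect and unrecorded factor; none comes from the protocol. They mark what the check cannot detect and do not forecast the AI's error. The primary analysis is not invalid. What changes is the conclusion that it can carry, and correcting that is cheap.

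**What to change.** Keep the comparison under Primary study endpoints as prognostic validation, and limit the primary conclusion to prognosis under the regimen received. Reword three places to match: primary objective item 1; the Study description sentence on which regimen better prevents events, so far as it refers to the AI; and item 2 of the analysis of primary endpoints. Suggested wording: *the AI gives a predicted risk under each regimen; the difference between the two has not been validated as a treatment effect.*

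Optional and exploratory, on data already collected: in the test set, compare the AI's mean predicted difference with the propensity-score-adjusted observed difference, with intervals and a sensitivity analysis for unmeasured confounding.

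The cost is wording, plus one analysis if the option is taken; no new patients or visits are needed. The study gives up a treatment-choice claim as a primary conclusion. The optional check is imprecise. Under the assumptions of step 2, its 95% half-width is 5.8–6.5 points with 400 test patients (an assumed 20% of 2,000), 3.6–4.1 with 1,000 and 2.5–2.9 with 2,000, all wider than the assumed effect. It adjusts for recorded factors only, so it shares the AI's error when a confounder is unrecorded: in the strongest case with g > 0 the adjusted difference is +1.4 to +1.6, close to the AI's own value. It therefore does not license a regimen-choice claim.

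### The primary endpoint compares the AI only with observed outcomes, so it can show absolute predictive performance but not benefit over a simple predictor from routine baseline data.

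*Protocol*

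**What the plan says.** The synopsis section on study objectives gives the primary aim as to "develop an AI that will search for and retrieve similar cases to each patient, and assess benefits of the technology". Its second numbered objective is "To prove AI's merit in predicting prognosis by applying it to different patient groups".

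Under primary study endpoints, the AI predicts 11 outcomes up to 3 months after onset for each antiplatelet regimen. An investigator unaware of the regimen "will evaluate the same outcome variables separately and compare the results with those predicted by the AI".

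Three other places bear on how the AI is tested:

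- The study description says "The performance of the AI will be verified with independent test sets".
- Item 5 of the analysis of primary endpoints says that the AI-based analysis "will need to have its results clearly verified as to their quality/accuracy". After a warning about overfitting it adds "Therefore, a new dataset will be created to evaluate the performance of the AI".
- Item 4 of the same list refers to "verification processes of the model to simultaneously consider clinical/image information". No version of the model without images is described.

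The study description also mentions other statistical methods, but as part of the build: "an AI, using various advanced statistical methodologies and deep learning techniques will be developed". The one head-to-head comparison in the protocol is the secondary endpoint, which compares two treatment groups and not two predictors.

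**The concern.** Merit and benefit are naturally read as comparative: better than what a physician could already obtain from information at hand. The protocol expects physicians to use the output when choosing an antiplatelet agent, so that is the practical question. The fixed comparison has one predictor and one truth. Independent test data protect it against overfitting, but they supply no benchmark.

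Two things are at stake. First, several of the 11 outcomes, such as symptomatic intracranial haemorrhage or haemorrhagic vascular death, may be infrequent within 90 days. A loosely chosen accuracy figure could then be high with little predictive content. Second, even a sound measure such as the AUC, judged only against chance, sets a low bar that a plain regression on baseline variables might also clear. A report could then claim benefit of the technology on evidence that speaks only to absolute performance.

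**Working it through.** **The plan's own figure.** The target is 1,000 + 1,000 = 2,000 patients. The protocol ties no event rate, accuracy target, alpha or power to it, so there is no calculation to reproduce. Every incidence, AUC, correlation and test-set size below is an assumption, used for illustration.

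**Step 1: what a predictor with no patient information scores.** At incidence p, predicting no event for everyone agrees with the observed outcome in 1 − p of patients. A constant forecast equal to p has Brier score p(1 − p).

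| Assumed incidence | Agreement of the no-event rule | Brier score of the constant forecast |
|---|---|---|
| 0.5% | 99.5% | 0.005 |
| 1% | 99% | 0.0099 |
| 5% | 95% | 0.0475 |
| 10% | 90% | 0.09 |
| 20% | 80% | 0.16 |

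Neither a high agreement nor a small Brier score can be interpreted without a reference value.

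**Step 2: precision of a paired comparison.** Assume 500 test patients, 10% incidence (50 events, 450 non-events) and AUC A = 0.75. The Hanley-McNeil terms are:

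- A/(2 − A) = 0.75/1.25 = 0.600
- 2A²/(1 + A) = 1.125/1.75 = 0.643
- Variance = [0.75 × 0.25 + 49 × (0.600 − 0.5625) + 449 × (0.643 − 0.5625)] / (50 × 450) ≈ 0.00169, so SE ≈ 0.041

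With the same SE for the reference model and an assumed correlation of 0.6 between the two AUC estimates, the SE of the difference is 0.041 × √(2 × (1 − 0.6)) ≈ 0.037. The 95% half-width is 1.96 × 0.037 ≈ 0.07. Power to detect a gain of 0.05 is Φ(0.05/0.037 − 1.96), about 27%. A gain of about 0.10 is needed for 80% power, since (1.96 + 0.84) × 0.037 ≈ 0.10.

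**Step 3: beating chance and beating a reference are different tests.** Assume AI AUC 0.75, reference AUC 0.70, correlation 0.3 to 0.7 and two-sided 0.05. The variance of the difference is s₁² + s₂² − 2r·s₁·s₂, with each SE from Hanley-McNeil.

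| Test patients | Incidence | Power, AUC above 0.5 | Power, AI above reference |
|---|---|---|---|
| 2,000 | 1% | 98% | 10–17% |
| 2,000 | 5% | about 100% | 30–60% |
| 2,000 | 10% | about 100% | 52–87% |
| 2,000 | 20% | about 100% | 79–99% |
| 400 | 1% | 42% | 5–7% |
| 400 | 20% | about 100% | 23–47% |

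The 2,000-patient rows treat the whole target sample as test data, which leaves none of it for training. The row with 400 patients and 1% incidence has only 4 events, so the normal approximation is rough there.

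**Reading the results.** Passing the test against chance says little about passing the test against a reference. The comparison with a reference is usable only for the commoner outcomes, and even there it is imprecise at moderate test-set sizes.

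**The case against.** **The statistical analysis plan may cover this.** Metrics, thresholds and benchmark models are often placed there, and that document is not at hand. This stands in part: the absence of a metric or threshold is not a fault here, and no one can say that the trial as a whole lacks a benchmark. However, what the primary endpoint compares is a protocol matter, and the protocol states it. A benchmark added elsewhere would not, as the text is written, be part of that endpoint.

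**Added value is not a stated objective.** A reader might infer that the trial is meant to prove that deep learning or imaging adds something, and that it cannot. The protocol does not support this reading. Objective 2 concerns predicting prognosis in other patients, and nothing promises superiority over regression or an incremental gain from images. Good discrimination and calibration in independent data would be valid evidence of some merit.

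**Percent agreement is never named.** This is correct. The objectives and item 2 of the primary analysis speak of probabilities, and the no-event rule has an AUC of only 0.5. Step 1 therefore warns against one reading of accuracy and does not describe what the plan prescribes.

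**The data would allow the comparison.** This too is correct. The planned library holds clinical and imaging information, so a reference model could be fitted and scored. The gap is in the stated comparison and not in the data.

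**A superiority rule would be underpowered.** Steps 2 and 3 bear this out, and it shapes the fix. The choice of reference is also open: an existing score or clinician judgement could serve.

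**Conclusion.** The point holds in a limited form. The protocol sets out to prove merit and assess benefits but fixes only a comparison of AI prediction with observed outcome. That comparison can establish absolute predictive performance in independent data. It cannot establish benefit over simple prediction from routine baseline data.

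The size can be shown only under assumptions. If percent agreement were used, a no-event rule would score 90% to 99.5% at incidences of 10% to 0.5%. With 2,000 test patients, 5% incidence and AUCs of 0.75 and 0.70, power is about 100% against chance but 30–60% against the reference.

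It would go too far to say that the primary question stays unanswered or that the trial cannot show any merit. This is a cheap improvement to a stated comparison and not a fatal flaw.

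**What to change.** Under primary study endpoints and in item 5 of the analysis of primary endpoints:

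1. Add a prespecified reference model, for example penalised logistic regression on regimen and routine baseline clinical variables without image features. Fit it on the same training patients as the AI and score it on the same test patients.
2. Report discrimination, Brier score and calibration for both models.
3. For the commoner outcomes (for example neurological deterioration and new ischaemic stroke, if event counts allow), report the paired AI-minus-reference difference with a confidence interval. Keep the rarer outcomes descriptive.
4. State that percent agreement is not the performance measure.
5. Do not make superiority over the reference the sole success rule. Claim benefit over simpler prediction only where the paired interval supports it. Otherwise limit objective 2 to absolute predictive performance.

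The cost is a few days of analysis on data already collected, plus protocol and analysis-plan wording. The downside is that the intervals will be wide (about ±0.07 in AUC at an assumed 500 test patients and 10% incidence) and may not support a claim of added benefit even if the AI is somewhat better.
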